## 1. BACKGROUND, OBJECTIVES, & STUDY DESIGN

Ankle syndesmosis disruption due to ankle trauma is associated with significant pain and disability.  Surgical stabilization procedures typically involve an internal fixation of the distal tibiofibular joint to restore the spatial relationship of the bony structures. Rigid fixation has traditionally been the technique of choice for stabilizing the syndesmosis; however, dynamic fixation options like the TightRope® system (Arthrex®, Naples, United States) have more recently demonstrated some advantage over rigid screw fixation techniques as they attempt to mimic the dynamic nature of the syndesmosis.  Tightrope or flexible fixation is still a non-anatomic reduction and stabilization technique and as such is only an approximation of the syndesmotic ligaments.

Anterior inferior tibiofibular ligament (AITFL) augmentation techniques using nonabsorbable suture materials (*Internal*Brace, Arthrex®, Naples, United States) have been used to supplement syndesmotic fixation in order to more accurately reconstruct the syndesmosis and restore native biomechanics.  Clinical research assessing the use of the *Internal*Brace as an additional stabilization method is lacking and the minimum required stability to achieve successful clinical and patient-reported outcomes remains unclear.

The primary objective of this study is to evaluate the quality of syndesmotic reduction as determined by weight bearing 3-D relative volumetric ratio between ankles in patients undergoing syndesmotic stabilization with and without an *Internal*Brace augmented repair of the AITFL to determine if the technique influences the reduction and postoperative stability of the syndesmosis. This will be compared at both 6-weeks and 3-months post-operation. Our

secondary objectives are 1) to determine whether the addition of the *Internal*Brace augmentation to the traditional TightRope fixation procedure improves short- and long-term patient-reported ankle function and generic health ratings and 2) to explore relationships between syndesmotic volume and patient-reported outcomes across groups.

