#### **Design**

We will use a prospective, two-arm, single-blind, randomized study design to conduct our pilot study. After informed consent, twenty patients will be randomized evenly into a traditional TightRope fixation group or a TightRope fixation with an AITFL augmentation group upon enrollment into the study. As this is a pilot study with a small sample size, block randomization will be used to reduce the risk of unequal group sizes between groups. A researcher who will not otherwise be involved in patient interactions will serve as the randomization coordinator for this trial. They will prepare a randomization schedule using the freely accessible tools available at www.randomization.com. The sequence generator uses block randomization procedures based on the number of interventions and patients needed in each block and creates a schedule based on the patient ID number. Due to the potential emergent nature of injuries involved in this study and a short time between enrollment and surgery, the surgeon may need to acquire the group allocation shortly after enrolling patients to be able to prepare for the surgery and so the schedule will be converted to a Google Document that can then be accessed by the surgeon/PI to reveal the intervention allocation. Since pre-operative and post-operative instructions are the same regardless of the procedure, the participants will be blinded to their intervention group until the completion of the study period.

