#### Withdrawal of Subjects

Participants will be withdrawn from the study if any of the following conditions exist:

- 1. Participant voluntarily withdraws from the study
- 2. Participant death

- 3. Participant who, in the opinion of the PI, would be compromised by continued study participation
- 4. Participant experiences an AE that, in the opinion of the PI, necessitates removal from the study, including unresolved SAE or death
- 5. Participant experiences an intercurrent illness, injury, or other reason that would, in the opinion of the PI, affect the assessment of clinical outcomes or the conduct of the study to a significant degree
- 6. Participant fails to comply with protocol requirements
- 7. Administrative reasons (e.g., PI decides to discontinue the study)

Under these conditions, all patient data will be immediately destroyed. During the consent process, participants will be informed of their right to withdraw from the study at any time for any reason and without prejudice to alternative treatment. For subjects lost to follow-up, the research team should attempt to contact the patient via phone a minimum of three times before considering them lost to follow-up. Participants who withdraw voluntarily or are discontinued by the PI will remain eligible for standard of care treatment by the PI and research team.

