#### STUDY RISKS & BENEFITS

#### Potential Risks to Study Participants & Risk Mitigation

- 1. Potential Risk: Loss of confidentiality
  - Risk Mitigation: All reasonable barriers will be in place to protect against the potential loss of confidentiality:
    - Data will be de-identified and data collection tools used to collect participants data will use unique subject ID numbers for identification
    - ii. Only generic demographic variables (e.g., age, sex, race) needed to evaluate participant characteristics will be captured in data collection
    - iii. Study materials and data collection tools will be kept in secure, locked areas only accessible to research team
    - iv. Electronic spreadsheets will only be accessible to assigned authorized personnel and will be password protected
    - v. Imaging (e.g., CT scan) will only be accessible by PI and clinical staff, and will be de-identified and labeled with subject ID numbers before

- volumetric assessments are completed
- vi. Study records will be continually monitored by study coordinators to ensure all data is de-identified. Any oversights will be corrected and research team members will be notified.
- 2. Potential Risk: Harm from radiation exposure during weight-bearing CT scan
  - Risk Mitigation: All reasonable limitations and protections against potential
    adverse health effects that may be associated with radiation exposure will be in
    place:
    - Patients that are not able to complete the WBCT necessary for volumetric assessments will be excluded
    - ii. During the consent process, the research team and the participant will discuss and assess the participant's exposure history and determine if the potential risk is acceptable for that participant. The participant will be given the opportunity to decline to participate in the study and not undergo the WBCT without any loss of benefits to which the participant was otherwise entitled.
- 3. Potential Risk: Surgery and surgical device implantation risks including infection and foreign body reactions or sensitivities. Other specific adverse effects noted for the study devices include: osteomyelitis surrounding the TightRope, failure of the implant resulting in re-diastasis, and painful aseptic osteolysis related to the wear of the FiberWire (not noted for XP). The InternalBrace does not have any known increased risk beyond potential material sensitivity.
  - Risk Mitigation: All reasonable limitations and protections against potential

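### Mandatory withdrawal after non-compliance, intercurrent events or adverse events may remove the patients most informative about stability, with possible bias of unknown size in either direction

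*Combined protocol and SAP*

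**What the plan says.** The Withdrawal of Subjects section opens with a mandatory rule: "Participants will be withdrawn from the study if any of the following conditions exist". Three of its seven conditions matter here.

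- Condition 4: "Participant experiences an AE that, in the opinion of the PI, necessitates removal from the study, including unresolved SAE or death".
- Condition 5: "Participant experiences an intercurrent illness, injury, or other reason that would, in the opinion of the PI, affect the assessment of clinical outcomes". The sentence goes on to include the conduct of the study, and it requires the effect to be a significant one.
- Condition 6: "Participant fails to comply with protocol requirements". No threshold or definition is given.

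The section then adds: "Under these conditions, all patient data will be immediately destroyed".

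The primary objective is "to determine if the technique influences the reduction and postoperative stability of the syndesmosis". It is measured by weight-bearing CT (WBCT) at 6 weeks and 3 months, with patient-reported outcomes (PROs) at those visits and at 6 months and 1 year (Study Procedures, step 9). Under Design, the schedule can be "accessed by the surgeon/PI to reveal the intervention allocation". The Statistical Analysis Plan specifies separate t-tests at each time point. It defines no analysis set and no rule for missing data.

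**The concern.** Conditions 4, 5 and 6 can all be met after the randomised operation, by events connected with what the trial measures. A patient who bears weight early departs from the post-operative directives and can meet condition 6. A patient who falls on the operated ankle can meet condition 5. Loss of reduction through the device is foreseen: the risk section lists "failure of the implant resulting in re-diastasis", and that would most naturally be handled as an adverse event under condition 4. These are patients in whom any extra stability from the augmentation would be tested.

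If such events differ between arms, or are judged differently between arms, those left in the comparison are a selected group. Conditions 4 and 5 turn on the opinion of a PI who knows the allocation. Blinded volume measurement does not help, because a withdrawn patient has no later scan to read. Both the volume ratio and the PROs are exposed.

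**Working it through.** **1. What a withdrawal costs.** From Study Procedures, step 9:

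| Time of event | WBCTs not done | PRO visits not done |
|---|---|---|
| Before 6 weeks | 2 of 2 | 4 of 4 |
| Between 6 weeks and 3 months | 1 of 2 | 3 of 4 |
| Between 3 and 6 months | 0 | 2 of 4 |

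Under the destruction sentence, everything already collected goes as well. Dropping that sentence alone would save the earlier records but not the visits in the table.

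**2. Is there a safeguard elsewhere?** None was found. The Statistical Analysis Plan has no as-randomised set, and no other section keeps a withdrawn patient in the comparison.

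**3. Size.** The plan states no power, effect size, SD or withdrawal rate, so there is no figure of its own to reproduce. What follows is illustration. Inputs from the documents: 20 patients split evenly (10 per arm), t-test, significance level 0.05. Assumptions: two-sided test, normal outcome with SD 1, higher meaning better, *k* patients removed.

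*Worst case: exactly the k lowest of 10 removed from one arm, no true effect.* The expected values of the three lowest of 10 standard normal observations are −1.539, −1.001 and −0.656. The full arm has expected sum 0, so the remaining mean is minus the removed sum, divided by 10 − k:

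- k = 1: 1.539 / 9 = 0.17 SD
- k = 2: (1.539 + 1.001) / 8 = 2.540 / 8 = 0.32 SD
- k = 3: (2.540 + 0.656) / 7 = 3.196 / 7 = 0.46 SD

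Rejection rates with no true effect come from simulation (100,000 to 200,000 trials per setting). For the worst case, repeat runs agree to about 0.3 percentage points.

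| Removal pattern | Mean shift | k = 1 | k = 2 | k = 3 |
|---|---|---|---|---|
| Worst k, one arm | 0.17 / 0.32 / 0.46 SD | 7.5% | 11.6% | 16.8% |
| Random k, one arm | none | about 5% | about 5% | about 5% |
| Most extreme k in either tail, one arm | none | 4.9% | 4.4% | 3.7% |
| Worst k, both arms | none | about 7% | about 9% | about 11% |

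*With a true benefit.* A difference of 1.32 SD is what 10 per arm detects with about 80% power; it is an assumption and is not in the documents. Removing the worst 1 or 2 controls lowers power to about 70% or 58%.

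*How an effect could disappear.* Suppose 20% of control ankles and no augmented ankles failed, each failure lowering the outcome by 2 SD, with no other difference. The difference among all randomised patients is 0.20 × 2 = 0.4 SD. If every failure is withdrawn, it is 0. If the augmented arm lost its worst ankles instead, the bias would run the other way.

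**The case against.** The strongest points on the other side are these.

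- **Condition 5 is narrower than it first looks.** It needs a significant effect and a PI judgement. An ankle that loses reduction without any new event is the outcome itself; nothing has impaired its assessment. A reader might infer that condition 5 requires every failed ankle to be withdrawn. The wording does not say so. This objection stands, and it is why condition 4 belongs in the point.
- **The large figures come from an extreme pattern.** They need the removed patients to be exactly the worst, in one arm, in one tail. The volume ratio can depart from 1 in either direction, so the worst ankle need not have the lowest value. This stands: random or symmetric removal produces no shift.
- **Some condition 5 cases are legitimate.** The ratio uses the uninjured contralateral ankle as reference. A new injury there can invalidate the ratio, so simply deleting the condition and analysing every scan would introduce a different error. This stands and shapes the fix.
- **This is a 20-patient pilot.** That carries less weight, because the plan tests differences between groups at 0.05, and with 10 per arm one patient matters.

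The objections leave intact the mandatory wording, the undefined non-compliance trigger, the unblinded judgement and the absence of any rule keeping these patients in follow-up.

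**Conclusion.** The point holds as a risk created by the rule as written. Conditions 4, 5 and 6 can end follow-up for reasons related to reduction and stability, and nothing in the analysis plan compensates. The resulting bias could favour either arm, and its size cannot be derived from the documents.

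A reader might infer that the arms will no longer be as randomised, or that the trial's false-positive rate is 16.8%. Neither is supported. No withdrawal or failure rate is given, the number and selection of removed patients are assumptions, and the figures of 7.5%, 11.6% and 16.8% mark a worst case for removal from one arm. The change should be made, and made prospectively, because scans not taken and data destroyed cannot be recovered.

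**What to change.** In Withdrawal of Subjects, separate leaving the study from leaving follow-up and analysis:

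1. Record non-compliance and intercurrent illness or injury with date and reason, and stop treating them as grounds for withdrawal. The WBCTs and PROs already planned are still sought where the participant agrees and can complete them, and the participant is analysed in the allocated arm.
2. After a condition 4 adverse event, apply the same continued follow-up where the participant agrees and the PI has no safety concern. Voluntary withdrawal and removal by the PI for safety stay as they are.
3. Replace immediate destruction with retention of data already collected, as far as consent allows.
4. If a new contralateral ankle injury makes the reference volume invalid, treat the volume ratio as missing from then on, but keep that participant's PROs and earlier scans.
5. Report these events by arm, with reasons.

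The cost is protocol wording and an IRB amendment; no visits are added to those already scheduled. The downside is somewhat more spread, because some retained outcomes will reflect re-injury or non-compliance.

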#### 2. STUDY PROCEDURES

Prospective patients will enter the clinic or hospital associated with the study doctor seeking care after ankle trauma. Patient will be moved through clinic/hospital workflow as normal. Once the patient elects to undergo syndesmotic stabilization surgery and is over 18 years of age, study protocol will be triggered as follows:

1. The study doctor will do an initial clinical screening for open fractures or fractures that would require a posterolateral approach during his examination, and if present, the patient will be excluded. If patients are not excluded at this point, the study doctor or another

member of the research team will enter the room and work through the informed consent process with the goal of obtaining the consent. Patient will have ample opportunity to read through documents to their desire. Patient will be asked if they are literate and speak English comfortably and excluded if they do not answer yes to both questions.

- 2. Once the consent is signed, a research team member will review patient's medical history for presence of other exclusion factors: previous ankle surgery, or any contralateral foot or ankle injury. If any exclusion factor is present, consent documents will be shredded.
- 3. If no exclusion factors are present at this point, the following will occur:
  - a. The patient will be issued a participant ID number and will complete the preoperative patient-reported outcomes (PROs) related to their perceived ankle function (The Foot and Ankle Outcome Score) and generic health status (SF-36). These will be administered by a research team member by using either paper format, or a tablet computer through a survey administration software called Surgical Outcome System (SOS).
  - b. The participant ID will be used by the study doctor to verify their randomized group allocation schedule generated by block randomization procedures described above and will be scheduled for their respective surgery.
- 4. Patient will follow typical pre-operative procedures. During the procedure, the patients will be in a supine position so that the fibula and the lateral ankle ligaments can be exposed. The integrity of the AITFL will be examined by the study doctor, and if disrupted the participant will be included in the study and will undergo either the traditional TightRope fixation procedure or the double stabilization procedure (TightRope fixation plus *Internal*Brace augmentation) as assigned and performed by the

- study doctor. If AITFL disruption is not confirmed at this point, the patient will be excluded from the study; however, will still undergo the appropriate stabilization procedures necessary for treating their traumatic injury. If patients are excluded at this point, they will be informed post-operatively, and all study documents will be shredded.
- 5. If participants are not excluded and are assigned to the traditional TightRope fixation group: the fibular fracture will be stabilized with fixation and the plate will be applied laterally to the fibula. The syndesmosis is directly reduced and held in a stable position with the TightRope device. The syndesmosis is then restressed and examined to ensure that it is stable and reduced.
- 6. If participant is not excluded and is assigned to the TightRope fixation plus *Internal*Brace augmentation group: the FiberTape portion of the *Internal*Brace will be threaded through the distal fibular plate which will then be applied. The fibular fracture will be stabilized with fixation and the plate applied laterally to the fibula. The syndesmosis will be directly reduced and held in a stable position with the TightRope device. A 3.4 mm drill and 4.75 mm tap are used to make a small hole in the distal tibia at the anatomic origin of the anterior inferior tibiofibular ligament. A 4.75 mm SwiveLock anchor is then used to set the tension of the AITFL repair over the top of the torn AITFL ligament. The syndesmosis is then restressed and examined to ensure that it is stable and reduced.
- 7. Pre-operative PRO data for all eligible participants will be entered into a spreadsheet by a research team member along with basic demographic information (age, biological sex, height, weight, race), involved side (right or left ankle), type of procedure (traditional or traditional plus augmentation), and any relevant surgical notes.

- 8. All participants will be given the same post-operative directives regarding treatments and care which includes being non-weightbearing and immobilized for the first two weeks after surgery. At this point, the patients will begin a physical therapy program incorporating passive modalities and gentle range-of-motion exercises. Patients will remain non-weightbearing in a post-operative cam boot for the next 4-6 weeks.

#### **Consent Process and Documentation**

The study doctor or another research team member will complete the entire consent process. Potential participants will be identified in the clinic or hospital. Once the subject has signed the surgical consent, the study will be presented and explained to them. After receiving detailed information regarding the study, objectives, logistics, inclusion/exclusion criteria, risks and potential benefits, they can then choose to sign the consent form once all their questions have been answered. The signed consent form will represent documentation that the consent process took place. The documentation will be stored in a locked file cabinet in the secured

research office. Patient will be informed that: data will be kept in excel spreadsheets only accessible to authorized study personnel on password protected computers; Identifiers will be kept until the end of the study, and data will be destroyed at the soonest possible time; Identifiers and data will be kept for the study period and only necessary personnel will have access to data.

#### 3. OUTCOMES & DATA

## **Primary Outcomes**

3D Syndesmotic Volume: Volumetric assessment of the distal syndesmosis will be performed with the WBCT using the CubeView software (CurveBeam, Warrington, PA). The software can calculate 3D volume amounts using cross-sectional imaging.

Measurements will start from the joint line and extend proximally, and will be performed by research staff blinded to the surgical procedure and trained by the study doctor.

#### Patient-Reported Outcomes:

- The Foot and Ankle Outcome Score (FAOS) will be used to assess participants' perceived ankle function.  It is a 42-item questionnaire with five subscales measuring pain, other symptoms including swelling, stiffness and range of motion, activities of daily living, sport and recreation, and foot and ankle-related quality of life and has demonstrated high internal consistency with subscales ranging from α = 0.88-0.97, acceptable test-retest reliability, and validity.  Items are scored on a 5-point Likert scale from *no* to *extreme*. Scores are totaled for each subscale and transformed into percentages, with 100% being representative of no functional loss.
- The SF-36 will be used to assess generic health ratings as it has demonstrated good reliability (ICC = 0.87) and construct validity. It is a 36-item questionnaire

assessing physical functioning, social functioning, role limitation caused by physical problems and emotional problems, bodily pain, mental health, energy, and general perceptions of overall health which combine to form the physical component summary (PCS) and the mental component summary (MCS). The norm-based standardized versions are based on a population mean of 50 and a standard deviation of 10 and will be used for analysis to allow for easy comparison with population norms.

## Adverse Events (AE) Definitions & Reporting

The research team will collect all adverse events (AE) during the study from the time of enrollment until the patient exits the study. The following definitions are intended to assist the research team in the identification of AEs. The research team will follow applicable regulatory requirements to report AEs to regulatory authorities and to the IRB.

Adverse Event (AE): An AE is any symptom, sign, illness or experience that develops or worsens in severity during the course of the study whether it is related or unrelated to the investigational device or its use. An AE need not be symptomatic to be reportable, e.g., device disruption detected on imaging that would require treatment, or psychological distress or discomfort associated with survey instruments.

Serious Adverse Event (SAE): An SAE is any AE that is:

- Fatal
- **Life threatening:** the participant is at risk of death (could have died without intervention) at the time of the event. This does not apply to any *hypothetical* risk of death if the AE were more severe or were to progress.
- Require or prolongs a hospital stay: Greater than 1 day (24 hours)

